1.6	27 Nov 22	
Updates throughout SAP to make clear results for ELDP and CT-proET-1 will not be reported in the CSR
 
Updates to the eGFR part of the Analysis of Secondary Objectives Other Than UACR section
 
Updates to the Extent of Exposure section
 
Updates to the Fluid-Related Measures section
 
Updates to the Interim Analysis section
 
Updates to the Analysis Sets part of Appendix B to clarify the interim analysis plan

1.7	07 Dec 22	
Update to the baseline disease characteristics part of the Demographic and Other Baseline Characteristics section
 
Updates to the Copy Reference Analysis section and the Jump to Reference Analysis section

2.0	07 Dec 22	Finalised version
2.1	05 Feb 23	
Updates to the Echocardiography Assessment of Cardiac Structure and Function section
 
Creation of new Global/Country Situation Summaries section from the previous COVID-19 Analysis and Ukraine/Russia Crisis Analysis sections
 
Updates to the Protocol Deviations section
 
Updates to the Primary Estimand for Primary Objective section
 
Updates to the Primary Analysis of Primary Objective section, including the sensitivity analyses part and the subgroup analyses part
 
Updates to the Tipping Point Analysis section
 
Updates to the Jump to Reference Analysis section; removal of the Copy Reference Analysis section and the BOCF-like Analysis section
 
Updates to the Supplementary Analysis of Primary Objective section
 
Updates to Extent of Exposure section

Parexel International

AstraZeneca
D4325C00001

Statistical Analysis Plan

Version No.	Effective Date	Summary of Change(s)
2.2	21 Feb 23	
Updates throughout SAP to make clear results for ET-1, copeptin and cortisol will not be reported in the CSR
 
Updates throughout SAP to remove loss to follow up as an ICE and to include death as an ICE
 
Updates to the Pharmacodynamics section within the Exploratory Variables section
 
Updates to the Study Period section
 
Updates to the Treatment Compliance section
 
Updates to the Null Hypothesis for Primary Objective and Related Secondary Objective section
 
Updates to the Primary Estimand for Primary Objective section
 
Updates to the subgroup analyses part of the Primary Analysis of Primary Objective section
 
Updates to the Tipping Point Analysis section
 
Updates to the Jump to Reference Analysis section
 
Updates to the Supplementary Analysis of Primary Objective section
 
Updates to the eGFR part of the Analysis of Secondary Objectives Other Than UACR section
 
Updates to Extent of Exposure section
 
Updates to Adverse Events section
 
Updates to Changes in the Conduct of the Study or Planned Analysis section

Version No.	Effective Date	Summary of Change(s)
2.3	16 Mar 23	
Updates throughout SAP to make clear results for NT-proBNP will not be reported in the CSR
 
Updates throughout SAP for how the second administrative interim analysis will be triggered
 
Updates to the dose-response relationship secondary objective endpoints text in the Secondary Objectives section
 
Updates to the Clinical Safety Laboratory Assessments section
 
Updates to the Software section
 
Updates to the Null Hypothesis for Primary Objective and Related Secondary Objective section
 
Dose-response Testing for the Dose-response Relationship Secondary Objective removed
 
Updates to reformulate the dose-response relationship secondary objective part of the Analysis of Secondary UACR Objectives section
 
Updates to the Extent of Exposure section
 
Updates to the Clinical Laboratory Evaluation section
 
Updates to the Pharmacokinetics section
 
Updates to the Analysis Sets section of Appendix B

2.4	30 Mar 23	
Updated section 4.2.2 to specify the list of variables that are expected to be skewed.
 
Updated section 4.6 to change “plasma concentration measurement post-randomisation” to “plasma concentration measurement post-treatment” to be in line with CSP.
 
Updated sections 4.10.2.2 and 4.10.3 to replace continuous covariates of baseline eGFR (serum creatinine) by baseline eGFR strata (≤ 45 versus > 45 mL/min/1.73 m²).
 
Updated section 4.6 to remove the statement “all measurements for an included participant will be considered” from the last paragraph of the definition of the Pharmacokinetic Analysis Set.
 
Updated section 4.15 to add deviations with CSP v3.0

3.0	05 May 2023	
Updated section 4.10.3 to consider continuous covariates of baseline eGFR (serum creatinine) instead of baseline eGFR strata (≤ 45 versus > 45 mL/min/1.73 m²).

LIST OF ABBREVIATIONS

Abbreviation / Acronym	Definition / Expansion
ABPM	ambulatory blood pressure monitoring
ACEi	angiotensin-converting enzyme inhibitor
AE	adverse event
AIC	Akaike's Information Criterion
ALT	alanine aminotransferase
ANCOVA	analysis of covariance
ARB	angiotensin receptor blocker
AST	aspartate aminotransferase/transaminase
BIS	bioimpedance spectroscopy
BMI	body mass index
BNP	B-type natriuretic peptide
BOCF	baseline observation carried forward
BP	blood pressure
BUN	blood urea nitrogen
CI	confidence interval
CKD	chronic kidney disease
COVID-19	Coronavirus Disease 2019
CSP	Clinical Study Protocol
CSR	Clinical Study Report
CT-proET-1	C-terminal pro-endothelin-1
DAE	adverse event leading to the discontinuation of study intervention
DBL	database lock
DKD	diabetic kidney disease
DM	diabetes mellitus
ECG	electrocardiogram
eCRF	electronic case report form
eGFR	estimated glomerular filtration rate
ELDP	endothelin-like domain peptide
ET-1	endothelin-1
FAS	Full Analysis Set
HF	heart failure
ICE	intercurrent event
IPD	important protocol deviation
LLOQ	lower limit of quantification
LVEF	left ventricular ejection fraction
MAR	missing at random
MCT	multiple contrast test
MedDRA	Medical Dictionary for Regulatory Activities
MI	multiple imputation
MMRM	mixed model for repeated measures
MNAR	missing not at random
MRA	mineralocorticoid receptor agonist
NT-proBNP	N-terminal pro-B-type natriuretic peptide
PD	pharmacodynamic(s)
PEY	participant exposure year

Abbreviation / Acronym	Definition / Expansion
PK	pharmacokinetic(s)
PPS	per protocol analysis set
PT	preferred term
QT	QT interval
QTcF	QT interval corrected using Fridericia's formula
SAE	serious adverse event
SAP	statistical analysis plan
SARS-CoV-2	severe acute respiratory syndrome coronavirus 2
SGLT2	Sodium-glucose co-transporter 2
SoA	Schedule of Activities
SoC	standard of care
SOC	system organ class
TEAE	treatment-emergent adverse event
TESAE	treatment-emergent serious adverse event
TLF	tables, listings and figures
UACR	urinary albumin to creatinine ratio
ULN	upper limit of normal
URC	Unblinded Review Committee
WHO-DD	World Health Organization - Drug Dictionary

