6.3 Measures to Minimise Bias: Randomisation and Blinding

All participants will be centrally assigned to randomised, blinded study intervention using an Interactive Response Technology/Randomisation and Trial Supply Management (IRT/RTSM). Before the study is initiated, the telephone number and call-in directions for the IRT and/or the log in information and directions for the RTSM will be provided to each site.

Participants will be stratified by diabetes (DKD versus non-DM CKD) and baseline eGFR (below or equal versus above 45 mL/min/1.73m²) at the time of randomisation to ensure an approximate balance between treatment arms within each sub-population.

- Stratum 1: DKD participants with eGFR \leq 45 mL/min/1.73m².
- Stratum 2: DKD participants with eGFR $>$ 45 mL/min/1.73m².
- Stratum 3: non-DM CKD participants with eGFR \leq 45 mL/min/1.73m².
- Stratum 4: non-DM CKD participants with eGFR $>$ 45 mL/min/1.73m².

The number of randomised participants in each stratum will be monitored to ensure that the non-DM CKD sub-population is approximately 30 to 50% of the total number of participants randomised in the study.

Study intervention will be dispensed at the study visits summarised in the SoA (Table 1). Returned study intervention should not be re-dispensed to the participants.

The IRT/RTSM will provide to the investigator(s) or pharmacists the kit identification number to be allocated to the participant at the dispensing visit.

Routines for this will be described in the IRT/RTSM user manual that will be provided to each centre.

The randomisation code should not be broken except in medical emergencies when the appropriate management of the participant requires knowledge of the treatment randomisation. The investigator documents and reports the action to AstraZeneca, without revealing the treatment given to participant to the AstraZeneca staff.

AstraZeneca retains the right to break the code for SAEs that are unexpected and are suspected to be causally related to an investigational product and that potentially require expedited reporting to regulatory authorities. Randomisation codes will not be broken for the planned analyses of data until all decisions on the evaluability of the data from each individual participant have been made and documented.

The following personnel will be unblinded as to the exact content of investigational treatments (ie, the randomisation code):

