9.4.2.2 Secondary Endpoints

The change in UACR for zibotentan 0.25 mg combined with dapagliflozin 10 mg versus dapagliflozin 10 mg monotherapy from baseline (Visit 2) to Week 12 (Visit 7) will be assessed. A MMRM model similar to that described for the primary endpoint will be fitted.

The dose-response relationship between different doses of zibotentan/a fixed dose of dapagliflozin and UACR reduction will be characterised by assessing the UACR reduction analysed in primary and first secondary objective.

The change from baseline (Visit 2) to Week 12 (Visit 7) in office systolic and diastolic BP will be assessed for doses of zibotentan combined with dapagliflozin 10 mg compared to dapagliflozin 10 mg monotherapy.

The effect of different doses of zibotentan and dapagliflozin in combination on eGFR will be determined from the change in eGFR from baseline to Week 1, Week 12, and Week 14, and from Week 1 to Week 12.

These secondary variables of BP and eGFR will be analysed using ANCOVA, adjusting for stratification factors, treatment arm, and baseline. The FAS will be used for these analyses. More details will be provided in the SAP.

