For continuous variables, descriptive statistics will include the number of non-missing observations (n), mean, standard deviation (SD), median, minimum and maximum. For log-normal variables, the geometric mean (GeoMean) and coefficient of variation (CV) will be presented in addition to those already specified for continuous variables. Continuous data that are expected to be skewed (e.g. duration of exposure, time on study and laboratory variables) will be presented in terms of the maximum, upper quartile, median, lower quartile, minimum and number of observations. The minimum and maximum will be reported to the same number of decimal places as the raw data recorded in the database. The mean, median, lower quartile and upper quartile will be reported to one more decimal place than the raw data recorded in the database. The SD will be reported to two more

decimal places than the raw data recorded in the database. In general, the maximum number of decimal places reported shall be four for any summary statistic.

Categorical variables will be summarised using frequency counts and percentages. Percentages will be presented to one decimal place. Percentages will not be presented for zero counts. Percentages will be calculated using the number of non-missing observations as the denominator, unless otherwise specified in the TLF mock shells. If sample sizes are small, the data displays will show the percentages, but any textual report will describe frequencies only.

P-values greater than or equal to 0.001, in general, will be presented to three decimal places. P-values less than 0.001 will be presented as “<0.001”.

Confidence intervals will be presented to one more decimal place than the raw data.

Data will be summarised by visit, as appropriate. For information on analysis visit windows, please refer to Section 4.2.3

‘Baseline’ is defined as the last non-missing value obtained prior to or on the same date as the administration of the first dose of study treatment, unless otherwise stated. For participants without a first dose, the last non-missing value obtained prior to or on the same date as the randomisation date will be used for ‘baseline’. ‘End of Study’ is defined as the last available post-treatment assessment. ‘Study Day’ will be calculated relative to the date of first dose of study treatment i.e.:

if Assessment Date < Date of First Dose of Study Treatment, then

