4.10.3 Analysis of Secondary Objectives Other Than UACR

The secondary efficacy variables will be based on a similar estimand to the primary estimand for the primary objective in Section 4.10.2.1, with the variable and population-level summary updated to be relevant to the secondary efficacy variable specified.

Office systolic and diastolic BP

The change from baseline to Week 12 in office systolic and diastolic BP will be assessed for doses of zibotentan combined with dapagliflozin 10 mg compared to dapagliflozin 10 mg monotherapy. This will be analysed using the MMRM method specified in Section 4.10.2.2, adjusting for the same variables, though with baseline BP replacing baseline log(UACR). The FAS will be used for this analysis and BP will be evaluated on the original scale.

The results of each MMRM will be presented by treatment arm. A summary of change from baseline of office systolic and diastolic BP results will be presented by treatment arm and a by-participant listing of office systolic and diastolic BP results at each visit will be provided. Plots of the mean office systolic and diastolic BP over time up to follow-up visit will be presented.

As a sensitivity analysis, a MMRM will be performed for office systolic and diastolic BP up to Week 12, analysed on the PPS, similarly to that described above.

eGFR

The effect of different doses of zibotentan and dapagliflozin in combination compared to dapagliflozin 10 mg monotherapy on eGFR will be determined from the change in eGFR from baseline to Week 1, from baseline to Week 12, from baseline to Week 14 and from Week 1 to Week 12. Change from baseline to Week 1, baseline to Week 12, baseline to Week 14 and Week 1 to Week 12 will be analysed using the MMRM methodology specified in Section 4.10.2.2. Change from baseline to Week 1, change from baseline to Week 3, change from baseline to Week 6, change from baseline to Week 9, change from baseline to Week 12 and change from baseline to Week 14 will be included in the model, adjusting for the fixed categorical effects of CSP version (Amendment 2 versus pre-Amendment 2), diabetes (DKD versus non-DM CKD), treatment visit, and treatment-by-visit interaction, plus the continuous covariates of baseline eGFR and baseline eGFR-by-visit interaction. The FAS will be used for these analyses and eGFR will be evaluated on the original scale.

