4.15 Changes in the Conduct of the Study or Planned Analysis

Echocardiography is included as an exploratory variable for efficacy assessments in the CSP but is included as a safety variable related to the safety objective in this SAP.

The CSP states that for the primary endpoint, no imputation is performed for UACR data that is treated as missing after the ICEs. If there are convergence issues with the MMRM proposed for the primary analysis, an ANCOVA with MI will be performed, meaning there is the possibility of imputation being performed. Regardless of the approach that will be taken for the primary analysis, sensitivity analyses will be performed that includes imputation for UACR data that is treated as missing after the ICEs.

The CSP states that the secondary variables of BP and eGFR will be analysed using ANCOVA but they will be analysed using a MMRM for consistency with the primary efficacy variable analysis, with an option for ANCOVA if none of the covariance structures converge.

The CSP does not include the phrase “or at a time selected by the sponsor” in relation to the first interim analysis for the planned timings of the interim analysis.

The CSP states that lost to follow-up is an ICE but it is not defined as an ICE in this SAP. It will be handled in the framework of missing data.

The CSP states that ABPM includes all participants in the FAS who have valid ambulatory BP data for change from baseline analysis, but as per SAP this analysis set will include all participants in the Descriptive Analysis Set who have valid ambulatory BP data for change from baseline analyses.

The CSP states that changes from baseline of ECG parameters will be listed, but as per SAP only the abnormalities (values outside the reference ranges) will be presented in the listings.

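### The eGFR model in SAP 4.10.3 omits the eGFR randomisation stratum that the protocol asks for, and SAP 4.15 does not declare it (minor)

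*SAP*

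**What the plan says.** Randomisation (Protocol 6.3) is "stratified by diabetes (DKD versus non-DM CKD) and baseline eGFR", with the eGFR cut at 45 mL/min/1.73 m². For the secondary variables, Protocol 9.4.2.2 states: "These secondary variables of BP and eGFR will be analysed using ANCOVA, adjusting for stratification factors, treatment arm, and baseline". Stratification factors and baseline are named as separate items.

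The eGFR part of SAP 4.10.3 lists CSP version, "diabetes (DKD versus non-DM CKD), treatment visit, and treatment-by-visit interaction" (apparently with a comma missing between treatment and visit), "plus the continuous covariates of baseline eGFR and baseline eGFR-by-visit interaction". No term for the eGFR stratum appears.

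The revision history shows how this came about. Version 2.4 (30 March 2023) says: "Updated sections 4.10.2.2 and 4.10.3 to replace continuous covariates of baseline eGFR (serum creatinine) by baseline eGFR strata". Version 3.0 (5 May 2023) says: "Updated section 4.10.3 to consider continuous covariates of baseline eGFR (serum creatinine) instead of baseline eGFR strata". On BP and eGFR, SAP 4.15 explains only that "they will be analysed using a MMRM for consistency with the primary efficacy variable analysis".

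**The concern.** The trial balances its arms on the eGFR stratum, and the protocol says the analysis will adjust for it. One secondary model does not, and the SAP section that exists to record such departures is silent. That section goes down to details such as which ECG values appear in listings, so a reader would expect to find this there.

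The two SAP revisions treat the stratum and continuous baseline as alternatives, whereas the protocol asks for both. If the stratum carries information on later eGFR beyond the model's baseline value, leaving it out leaves some explainable variation in the residual. The affected results are the eGFR comparisons of two zibotentan doses with dapagliflozin.

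**Working it through.** **1. Covariates side by side**

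| Source | eGFR stratum | Diabetes | Baseline of the endpoint |
|---|---|---|---|
| Protocol 9.4.2.2, BP and eGFR | yes | yes | yes |
| SAP 4.10.2.2, UACR | yes | yes | yes, with visit interaction |
| SAP 4.10.3, BP (same variables, baseline BP substituted) | yes | yes | yes, with visit interaction |
| SAP 4.10.3, eGFR | **no** | yes | yes, with visit interaction |

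The point rests on the current 4.10.3 text. The log only explains its origin.

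**2. Is the stratum redundant given continuous baseline?** SAP 4.2.2 defines baseline as the "last non-missing value obtained prior to or on the same date as the administration of the first dose of study treatment", normally the Visit 2 value. The stratum is fixed at randomisation, which precedes the first dose on Day 1 (Protocol 4.1). Chemistry goes to a central laboratory (Schedule of Activities), so a Visit 2 result is unlikely to be back in time. The stratum therefore presumably uses the screening sample, nominally four weeks earlier. The documents do not say so outright. If it does, the stratum is a coarse second reading of the same person's eGFR and helps to correct for noise in the Visit 2 reading.

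**3. The plan's own figures.** No SD, correlation or interval width is given for eGFR. The sample sizes reproduce within rounding: 150/0.9 = 166.7 (stated 166), 75/0.9 = 83.3 (stated 83), and 166 + 166 + 83 = 415.

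**4. Simulation with noisy readings.** Single-visit ANCOVA with 150/75/150 participants and 1,500 simulated trials per row. Assumptions, none from the documents: true eGFR Normal(47, 18) limited to 20–120; true-change SD 4; stratum set from a separate screening reading; within-person noise SD as shown (mL/min/1.73 m²). The SE is for 1.5 mg versus dapagliflozin.

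| Noise SD | SE, stratum only | SE, continuous only | SE, both | Stratum only / continuous | Both / continuous |
|---|---|---|---|---|---|
| 2 | 0.570 | 0.562 | 0.562 | 1.014 | 0.999 |
| 3 | 0.677 | 0.663 | 0.660 | 1.021 | 0.995 |
| 5 | 0.942 | 0.909 | 0.893 | 1.036 | 0.983 |
| 7 | 1.238 | 1.173 | 1.140 | 1.055 | 0.971 |

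Where change depends linearly on the measured baseline, so that a second reading adds nothing, both/continuous is about 1.001 and stratum only/continuous is 1.00 to 1.12.

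**5. A second set of assumptions.** True mean 45–50, SD 20–22, truncated at 20; within-person CV 6–12%; true-change SD 0–8%. Residual variance with the stratum divided by that without is 0.931 to 0.988. Taking square roots, √0.931 = 0.965 and √0.988 = 0.994, so intervals are 0.6% to 3.5% narrower. In a middle case (CV 8%, true-change SD 8%) the variance without the stratum is 2.8% larger, and 1 − √(1/1.028) = 1.4%.

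**6. Analytic check.** Adding one covariate multiplies the SE by √[(1 − R²) × df/(df − 1)], where R² is the share of the remaining variance that it explains. With df = 375 − 5 = 370 and R² = 0.02, this is √(0.98 × 370/369) = 0.991. Narrowing by 1% therefore needs the stratum to explain about 2% of what continuous baseline leaves. Break-even is near R² = 1/370 = 0.0027.

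**7. Absolute size.** With an assumed residual SD of 7.4 and 166 per arm, the 90% half-width is 1.645 × 7.4 × √(2/166) = 1.34 mL/min/1.73 m². A gain of 1.4% is 0.02.

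**8. Week 1 to Week 12.** A stratum effect that is constant over visits cancels between two post-baseline visits, and noise in the baseline reading cancels too. In simulation the variance ratio for this contrast was 1.00.

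**The case against.** The best defence is that the eGFR factor is already adjusted for in finer form. Continuous baseline with a visit interaction carries nearly everything a two-level cut can carry, diabetes is retained, and Protocol 9.4.2.2 leaves further detail to the SAP. The gain depends on noise levels that the documents do not give and on an inference about which sample sets the stratum. If the stratum term were instead derived from the analysis baseline, adding it would change residual variance by only 0.1% to 0.9%. All of this stands, and it is why the point is minor. It does not remove the mismatch with the protocol or the silence in 4.15.

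A reader might infer from the version 3.0 log entry that the swap itself widened the eGFR intervals. The documents do not support that. Version 2.4 had removed the continuous baseline that the protocol also requires, and version 3.0 put it back. In the first simulation table the stratum-only model has the larger SE in every row. The order reverses (ratio 0.985 to 0.996) only under an artificial pure step at 45 with no slope. Simply undoing version 3.0 would usually lose precision and would breach the protocol in another way.

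**Conclusion.** The eGFR MMRM departs from Protocol 9.4.2.2 by omitting a stratification factor, differs in this from the UACR and BP models, and the departure is undeclared. That much follows from the text alone.

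The statistical consequence is small. Relative to a model with both terms, intervals for change from baseline to Weeks 1, 12 and 14 would be roughly 0.5% to 3.5% wider. This assumes that the stratum comes from the screening eGFR and that within-person noise is moderate to large. At low noise the difference is negligible. The Week 1 to Week 12 endpoint is unaffected, so it would be wrong to count all four eGFR endpoints.

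Nor should the omission be read as a validity problem. Leaving a balanced prognostic factor out of a linear model causes no bias in the treatment contrast and, if anything, makes the standard errors slightly conservative. SAP 4.10.1.1 sets formal hypotheses only for UACR. Severity: minor.

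**What to change.** In the eGFR part of SAP 4.10.3, add the eGFR stratum as recorded in the IRT at randomisation (45 or below versus above 45) as a fixed effect. Keep continuous baseline eGFR and its visit interaction. Make the same change in the per-protocol sensitivity model. State that the term is the randomised stratum and is not re-derived from the analysis baseline.

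The cost is one model term and one degree of freedom with 415 participants planned, with no change to data collection. If the sponsor prefers the current model, add a line to SAP 4.15, before unblinding, stating that the eGFR stratum is omitted and why.
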